3.3. Exploratory Endpoints

Pharmacokinetic:

- Blood samples to determine 5-MeO-DMT and its metabolites (including bufotenine) plasma concentrations will be taken after dosing on Day 0.

Drinking Craving:

- Change in alcohol craving as measured by Alcohol Craving Questionnaire (ACQ) at Days 1, 7, 28, 56, and 84 compared to Baseline (pre-dose on Day 0)
- Alcohol cravings as measured by Craving Visual Analogue Scale (VAS)
- Alcohol withdrawal symptoms as measured by Clinical Institute Withdrawal Assessment (CIWA-Ar)
- Consequences of alcohol use as measured by Short Inventory of Problems (SIP)

Alcohol Use:

Using the Timeline Follow-Back (TLFB) interview, the following parameters of alcohol use in the 90 days before dosing and endpoint will be recorded:

- Percentage of Heavy Drinking Days (PHDD) in 85d prior D-3 (or start of detox) vs PHDD post-dosing measured on d14, d28, d56, d84.
- Percentage of drinking days (PDD) in 85d prior D-3 (or start of detox) vs PDD post-dosing measured on d14, d28, d56, d84.
- Mean Units per day (UPD): In 85d prior D-3 (or start of detox) vs UPD post-dosing measured on d14, d28, d56, d84.
- Abstinence: Percentage of Abstinent days (PAD) in 85d prior D-3 (or start of detox) vs PAD on d14, d28, d56, d84 (with biomarker verification).
- Longest duration (days) of continuous abstinence
- Number of days after BPL-003 dosing to first drink
- Number of days after BPL-003 dosing to first HDD (defined by UK government as >7 units a day for a woman and >9 units per day for a man)
- Average number of standard units of alcohol consumed per week in 85d prior D-3 (or start of detox) vs post-dosing measured on d14, d28, d56, d84 (and reported referencing UK risk levels)
- Maximum number of standard units of alcohol consumed on any one day

Correlation of PD effects with alcohol use and related symptoms

The correlation of the occurrence of a “complete mystical experience” and “ego dissolution”, measured by the MEQ30 and EDI, with improvement in alcohol use and craving (measured by AQC, TLFB, EtG, CDT)

Biomarkers

- Alcohol use as measured by EtG in urine at Days 1, 28, 56, 84 compared to Screening
- Alcohol use as measured by CDT in blood at Days 28 & 84 compared to Screening

Wellbeing

- Change in Montgomery–Asberg Depression Rating Scale (MADRS) at Days 28, 56, and 84 compared to Baseline
- Change in Clinical Global Impression Severity (CGIS) at Days 1, 28, 56, and 84 compared to Baseline

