9.17. Biomarkers

9.17.1. Ethyl Glucuronide

Ethanol is excreted from the body in a variety of ways, including

- Direct excretion of ethanol (5%-10%) in urine, sweat, and breath
- Metabolic excretion by conversion to acetaldehyde or acetic acid (>90%)
- Metabolic excretion by conversion to ethyl glucuronide (EtG) and ethyl sulfate (<0.1%), both of which are readily eliminated through urination

While most of these excretory products are detectable in urine for very short periods of time (<24 hours), EtG has a longer half-life and may be detectable in urine for up to 72 hours after consumption, depending on the dose taken prior to specimen collection. Although higher amounts of EtG might indicate greater alcohol consumption, the exact EtG number is influenced by several factors, including how recently alcohol was consumed. The presence of EtG in urine indicates only that the individual was exposed to ethanol at some point in the recent past before testing, typically within the preceding 72 hours.

There are some limitations to this test. It can produce a positive test from the mere exposure to alcohol that is present in many daily-use products, e.g., mouthwashes, breath sprays, foods prepared with or flavored with alcohol, and hand sanitizers. Therefore, a positive test should be confirmed either with another test or with verification from the patient that he or she did indeed drink alcohol. However, the EtG test accurately detects a person who recently consumed alcohol 70% or more of the time. One study showed that for moderate to heavy drinking, this value increases to 85% ([Shukla, 2017](#)).

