4.2.3 Exploratory endpoint(s)

Pharmacokinetic:

- Blood samples to determine 5-MeO-DMT and its metabolites (including bufotenine) plasma concentrations will be taken after dosing on Day 0.

Drinking Cravings and withdrawal:

- Change in alcohol craving as measured by Alcohol Craving Questionnaire (ACQ) at Days 1, 7, 28, 56, and 84 compared to Baseline (pre-dose Day 0)
- Alcohol cravings as measured by Craving Visual Analogue Scale (VAS)
- Alcohol withdrawal symptoms as measured by Clinical Institute Withdrawal Assessment (CIWA-Ar)

Alcohol Use:

- Using the Timeline Follow-Back (TLFB) interview, the following parameters of alcohol use in the 90 days before dosing and endpoint will be recorded:
 - Longest duration (days) of continuous abstinence
 - Maximum number of standard units of alcohol consumed on any one day
 - Number of Heavy Drinking Days (HDD)
 - Percentage of Heavy Drinking Days (PHDD) in 85d prior D-3 (or start of detox) vs PHDD post-dosing measured on d14, d28, d56, d84
 - Percentage of drinking days (PDD) in 85d prior D-3 (or start of detox) vs PDD post-dosing measured on d14, d28, d56, d84.
 - Mean Units per day (UPD): In 85d prior D-3 (or start of detox) vs UPD post-dosing measured on d14, d28, d56, d84.
 - Abstinence: Percentage of Abstinent days (PAD) in 85d prior D-3 (or start of detox) vs PAD on d14, d28, d56, d84 (with biomarker verification).
 - Number of days after BPL-003 dosing to first drink
 - Number of days after BPL-003 dosing to first HDD (defined by UK government as ≥ 7 units a day for a woman and ≥ 9 units per day for a man)
 - Average number of standard units of alcohol consumed per week in 85d prior D-3 (or start of detox) vs post-dosing measured on d14, d28, d56, d84 (and reported referencing UK risk levels)
- Consequences of alcohol use as measured by Short Inventory of Problems (SIP)
- Biomarkers:
 - Alcohol use as measured by Ethylglucuronide (EtG) in urine at Days 1, 28, 56, 84 compared to Screening
 - Alcohol use as measured by carbohydrate deficient transferrin (CDT) in blood at Days 28 & 84 compared to Screening

Pharmacodynamic

- The correlation of the occurrence of a “complete mystical experience” and “ego dissolution”, measured by the MEQ-30 and EDI, with improvement in alcohol use and craving (measured by ACQ, TLFB, EtG, CDT)

Wellbeing:

- Change in Montgomery–Asberg Depression Rating Scale (MADRS) at Days 28, 56, and 84 compared to Baseline

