14.7 Clinical laboratory evaluations

Data from haematology, coagulation, clinical chemistry and alcohol biomarkers at each planned assessment, and changes from baseline at each planned post baseline assessment, will be summarised by treatment.

Clinically significant abnormal laboratory tests will be listed. Frequencies of clinically significant postpose abnormal laboratory tests will be summarised.

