4.2 Analysis and reporting

The following will be calculated:

Scoring item	Calculation
Longest continuous number of abstinence (days)	Max number of continuous days where units=0
Maximum number of standard units of alcohol consumed on any one day	Max units where units >0
Number of Heavy Drinking Days (HDD)	Total days where units >=9 for men; Total days where units >=7 for women
Percentage of Heavy Drinking Days (PHDD) in 85d prior D-3 (or start of detox) vs PHDD post-dosing measured on d14, d28, d56, d84	% of the number of HDD (see above for definition) for 85d prior D-3 (or start of detox) vs % of the number of HDD D0-D14, D0-D28, D0-D56, D0-D84
Percentage of drinking days (PDD) in 85d prior D-3 (or start of detox) vs PDD post-dosing measured on d14, d28, d56, d84	% of the total days where units > 0 for 85d prior D-3 (or start of detox) vs % of the total days where units > 0 on D0-D14, D0-D28, D0-D56, D0-D84
Mean Units per day (UPD): In 85d prior D-3 (or start of detox) vs UPD post-dosing measured on d14, d28, d56, d84.	(sum of all units)/(85d prior to D-3) vs (sum of all units)/(D0-D14); (sum of all units)/(D0-D28); (sum of all units)/(D0-D56); (sum of all units)/(D0-D84)

Abstinence: Percentage of Abstinent days (PAD) in 85d prior D-3 (or start of detox) vs PAD on d14, d28, d56, d84	% of days where units=0 for 85d prior D-3 (or start of detox) vs % of days where units=0 on D0-D14, D0-D28, D0-D56, D0-D84
Number of days after BPL-003 dosing to first drink	Number of days until units >0 after D0 (dosing)
Number of days after BPL-003 dosing to first HDD (defined by UK government as ≥ 7 units a day for a woman and ≥ 9 units per day for a man)	Number of days until units ≥ 9 (male) or ≥ 7 (female) after D0 (dosing)
Average number of standard units of alcohol consumed per week in 85d prior D-3 (or start of detox) vs post-dosing measured on d14, d28, d56, d84 (and reported referencing UK risk levels)	Average number of standard units of alcohol consumed per week in 85d prior D-3 (or start of detox) vs post-dosing measured on d14, d28, d56, d84

5 Alcohol Craving Questionnaire (ACQ)

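### Percentage of abstinent days is defined as biomarker-verified, but the SAP computes it from self-report alone, with no rule linking EtG or CDT to it and no sample of either at Day 14

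*SAP*

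**What the plan says.** The protocol synopsis, Protocol 3.3 and SAP 4.2.3 all give the abstinence endpoint as baseline PAD "vs PAD on d14, d28, d56, d84 (with biomarker verification").

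SAP Appendix A, 4.2 gives the calculation. The row title leaves out the verification phrase. Baseline is the percentage "of days where units=0 for 85d prior D-3 (or start of detox"), set against the post-dose figure: "vs % of days where units=0 on D0-D14, D0-D28, D0-D56, D0-D84". Both come from TLFB units.

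The biomarkers have their own endpoints in Protocol 3.3: "Alcohol use as measured by EtG in urine at Days 1, 28, 56, 84 compared to Screening" and "Alcohol use as measured by CDT in blood at Days 28 & 84 compared to Screening". SAP 14.7 places them with the laboratory data: "Data from haematology, coagulation, clinical chemistry and alcohol biomarkers at each planned assessment" are summarised by treatment. They appear in Tables 14.3.4.2 and 14.3.5.4 and Listings 16.2.8.7 and 16.2.8.8. The TLFB table and listing shells have no biomarker column.

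Protocol 9.17.1 says that a positive EtG shows exposure at some point in the recent past, "typically within the preceding 72 hours". It also says that a positive result should be confirmed by another test or by the patient, because everyday products can cause one.

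**The concern.** The endpoint claims a property that its calculation cannot give it. This is more than missing detail, because Appendix A does state a rule and that rule uses self-report only. If a patient reports zero units for the three days before Day 28 and the Day 28 EtG is positive, PAD stays the same and no planned output pairs the two results.

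The study is open-label with no control arm, and Protocol 9.5 accepts that the TLFB is not precise day by day. EtG is a more objective check and is already being collected. At stake is whether a reader of the study report can tell how far self-reported abstinence was corroborated, and on which days. The Day 14 figure is the weakest, because the schedule cannot support the claim there.

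**Working it through.** The documents give no figure to reproduce. The check is whether any biomarker can enter PAD, and how many days EtG could cover if it did.

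**Step 1. Sampling days (Protocol Table 1).**
- EtG: Screening, Days 1, 28, 56, 84.
- CDT: Screening, Days -3, 28, 84.
- Haematology and chemistry, which supply the other relapse markers of Protocol 9.17.3: Screening, Days -3, 1, 28, 84.
- TLFB: collected at Days 14, 28, 56 and 84, among others.

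None of these biomarkers is sampled at Day 14.

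**Step 2. Days that a biomarker can change under the SAP rule.** The only input in Appendix A 4.2 is TLFB units, so the answer is 0 in every window.

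**Step 3. Days that EtG could check if a rule were added.** Windows are read as inclusive of Day 0, so D0-D84 has 85 days. Two readings of the 72 h look-back are used: (a) the 3 days before the sample; (b) the sample day plus the 3 days before. The Day 1 sample contributes only Day 0 under (a), and Days 0 and 1 under (b), because the rest of its look-back lies before the window.

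| Window | Days | Covered, (a) | Covered, (b) | Share |
|---|---|---|---|---|
| D0-D14 | 15 | 1 | 2 | 7-13% |
| D0-D28 | 29 | 1 + 3 = 4 | 2 + 4 = 6 | 14-21% |
| D0-D56 | 57 | 1 + 6 = 7 | 2 + 8 = 10 | 12-18% |
| D0-D84 | 85 | 1 + 9 = 10 | 2 + 12 = 14 | 12-16% |

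In D0-D84, 71 to 75 of 85 days cannot be checked by EtG. If the window starts at Day 1, the counts are 9 to 13 of 84 (11-15%).

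**Step 4. What the Day 1 sample can show.** Inclusion criterion 5 bars heavy drinking for 72 h and all alcohol for 24 h before dosing. Non-heavy drinking between 72 h and 24 h before dosing is therefore allowed, and part of that period lies inside the Day 1 look-back. A positive Day 1 EtG does not by itself show drinking after dosing.

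**Step 5. How far one confirmed discordant sample would move PAD.** A positive EtG shows at least one exposure in up to three days. In D0-D84 one sample moves PAD by 1/85 = 1.2 to 3/85 = 3.5 percentage points. If all three samples at Days 28, 56 and 84 were discordant, the movement would be 3/85 = 3.5 to 9/85 = 10.6 points.

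**The case against.** The best defence is that the parenthesis means corroboration reported beside PAD, and that the plan supplies it. EtG and CDT are endpoints in their own right, they feed the planned correlation with mystical experience, and SAP 19.1 promises complete listings. With at most 12 patients, someone could compare EtG and TLFB by hand. This is partly right: the biomarkers are neither ignored nor confined to one table. But it is not a planned analysis. Group summaries cannot pair a patient's sample with that patient's diary. Listings 16.2.8.7 and 16.2.8.8 cover only patients with clinically significant values, and the TLFB listing shell shows window totals, not days.

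Three stronger readings are tempting, and the documents do not support them.
- A reader might infer that the results will be labelled as verified. The Appendix A row title and the table and listing shells do not use that word. The mismatch lies between the endpoint lists and the calculation.
- A reader might infer that no biomarker at all bears on the Day 14 figure. The Day 1 EtG lies in D0-D14, though confounded as shown, and CDT takes several weeks to normalise (Protocol 9.17.2), so Day 28 CDT carries some information on earlier heavy drinking.
- A reader might infer an undeclared change that SAP section 17 should have listed. The protocol gives no verification algorithm and leaves detail to the SAP, and SAP 4.2.3 keeps the phrase. This is better described as an omission.

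**Conclusion.** The point holds. PAD is stated as biomarker-verified at four time points, is computed from self-report alone, and has no linking rule. At Day 14 the schedule could not support verification even with a rule. A linking rule would let EtG check 12-16% of D0-D84 and at most about 21% of any window.

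These shares assume samples on the nominal day and a full 72 h look-back. Visit windows of 2 or 4 days either way would shift them, and the protocol makes the look-back depend on the amount drunk. They count days within reach of a test and are not detection rates: the protocol says only that "the EtG test accurately detects a person who recently consumed alcohol 70% or more of the time". That figure concerns persons, so it is not multiplied into the day counts here.

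A reader might also infer that PAD is biased upward by a known amount. The documents give no rate of under-reporting, so no such size can be stated. PAD is one of several exploratory, descriptive alcohol-use measures with no hypothesis attached. No error rate, sample size or primary conclusion depends on it. It is still worth correcting, because the stated endpoint is wrong as it stands and the repair is cheap.

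**What to change.** 1. In SAP Appendix A 4.2, cross-tabulate EtG (positive or negative) at Days 28, 56 and 84 with the TLFB for the 72 h before each sample (zero units or any). Report the number of discordant patients, meaning EtG positive with TLFB zero.
2. Add a sensitivity PAD. Each discordant sample that is confirmed in the way Protocol 9.17.1 describes counts as at least 1 and at most 3 non-abstinent days, shown as a range (1.2 to 3.5 percentage points of D0-D84 PAD per sample). Unconfirmed positives stay in the cross-table but do not alter PAD, which respects the protocol's confirmation step.
3. Reword the endpoint in the synopsis, Protocol 3.3 and SAP 4.2.3: PAD is self-reported, with EtG concordance for the 72 h before the Day 28, 56 and 84 samples. Drop the verification claim for Day 14.

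The cost is wording in two documents, one small table and one sensitivity row. TLFB and EtG are already both collected on those three days, so no visit or sample is added. Two limits remain: unconfirmed or incidental EtG positives will leave some results ambiguous, and most days will still rest on self-report.

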9.1 Analysis datasets

All analysis datasets will be based on observed data, except as outlined in Section 12.2.

10 Treatment comparisons

The treatment comparison of interest is active between ascending dose levels.

11 General considerations for data analyses

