11.2 Conventions for summary statistics and data displays

The minimum set of summary statistics for numeric variables will be: n, mean, standard deviation (SD) (or standard error), median, minimum, and maximum. 95% confidence intervals (CI) will be presented where appropriate for data interpretation.

Categorical data will be summarised in frequency tables with n and percentage. Summaries of a categorical variable will include all recorded values.

The minimum and maximum values will be presented with the same number of decimal places as the raw data collected on the case report form (CRF) (or to 3 significant figures for derived parameters less than 100 and as integers for values more than 99). The mean and percentiles (eg median) will be presented using one additional decimal place. The standard deviation and standard error will be presented using two additional decimal places.

12 Data handling conventions

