12.1 Premature withdrawal and missing data

All patients who withdraw prematurely from the study or study drug will be included in the statistical analyses.

If a patient completes the treatment period but has missing data, then this will be made apparent in the patient listings. Missing data will not be imputed.

If the study is prematurely discontinued, all available data will be listed and a review will be carried out to assess which statistical analyses are still considered appropriate.

Data collected at unscheduled time points during the study will not be used in the summaries or data analyses. They will be included in the listings.

If time information (ie hours and/or minutes) for adverse events (AEs) or concomitant medication is missing, but the day is present, then the time will be calculated in days. If date information is partial or missing, then any derived times (eg AE start time from last study medication) will be listed as missing.

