Source: Listing 16.2.xx

Programming notes: For EDI and visual analogue scale, the first column will be "Score (mm)". Include all subscales as stated in appendix A

Template T_PD1a

Table 14.2.2.xx Summary of Timeline Follow-Back (TLFB) [intent-to-treat population]

Scoring Item	Treatment	Planned Relative Time	n	Mean	SD	Median	Min	Max	Change from Baseline					
									n	Mean	SD	Median	Min	Max
Longest continuous number of abstinence (days)	Treatment 1 (N=xx)		x	x.x	x.xx	x.x	x	x						
Max number of standard units of alcohol consumed on any one day	Treatment 1 (N=xx)	85 Days Prior Day-3	x	x.x	x.xx	x.x	x	x						
		Day 14	x	x.x	x.xx	x.x	x	x						
		Day 28	x	x.x	x.xx	x.x	x	x						
		Day 56	x	x.x	x.xx	x.x	x	x						
		Day 84	x	x.x	x.xx	x.x	x	x						
Number of Heavy Drinking Days (HDD)	Treatment 1 (N=xx)	85 Days Prior Day-3	x	x.x	x.xx	x.x	x	x						
		Day 14	x	x.x	x.xx	x.x	x	x						
		Day 28	x	x.x	x.xx	x.x	x	x						
		Day 56	x	x.x	x.xx	x.x	x	x						
		Day 84	x	x.x	x.xx	x.x	x	x						
Number of days after dosing to first drink	Treatment 1 (N=xx)		x	x.x	x.xx	x.x	x	x						
Number of days after dosing to first HDD	Treatment 1 (N=xx)		x	x.x	x.xx	x.x	x	x						
Average number of standard units of alcohol consumed per week	Treatment 1 (N=xx)	85 Days Prior Day-3	x	x.x	x.xx	x.x	x	x						
		Day 14	x	x.x	x.xx	x.x	x	x	x	x.x	x.xx	x.x	x	x
		Day 28	x	x.x	x.xx	x.x	x	x	x	x.x	x.xx	x.x	x	x
		Day 56	x	x.x	x.xx	x.x	x	x	x	x.x	x.xx	x.x	x	x
		Day 84	x	x.x	x.xx	x.x	x	x	x	x.x	x.xx	x.x	x	x
Percentage of Heavy Drinking Days (PHDD)	Treatment 1 (N=xx)	85 Days Prior Day-3	x	x.x	x.xx	x.x	x	x						
		Day 14	x	x.x	x.xx	x.x	x	x	x	x.x	x.xx	x.x	x	x
		Day 28	x	x.x	x.xx	x.x	x	x	x	x.x	x.xx	x.x	x	x
		Day 56	x	x.x	x.xx	x.x	x	x	x	x.x	x.xx	x.x	x	x
		Day 84	x	x.x	x.xx	x.x	x	x	x	x.x	x.xx	x.x	x	x
Percentage of Drinking Days (PDD)	Treatment 1 (N=xx)		x	x.x	x.xx	x.x	x	x	x	x.x	x.xx	x.x	x	x
Mean Units per Day (UPD)	Treatment 1 (N=xx)		x	x.x	x.xx	x.x	x	x	x	x.x	x.xx	x.x	x	x

Abstinence: Percentage of Treatment 1 (N=xx) x x.x x.xx x.x x x x x.x x.xx x.x x x

Abstinent Days (PAD)

Source: Listing 16.2.xx

Note: 85 Days Prior Day -3 = 85 Days Prior Day -3 (or start of detox)

Programming notes: Continued with all the timepoints (85 Days Prior Day-3, Day 14, Day 28, Day 56 and Day 84) for PDD, UPD and PAD

Template T_PD2

Table 14.2.2.xx Summary of Montgomery-Åsberg Depression Rating Scale (MADRS) [intent-to-treat population]

Question	Treatment	Planned Relative Time	n	Mean	SD	Median	Min	Max	Change from Baseline					

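### Days to first drink and to first heavy drinking day have no censoring rule, so as planned their means and medians describe only patients who had the event; maximum units has a related gap

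*SAP*

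**What the plan says.** SAP Appendix A, section 4.2, gives the scoring rule for each Timeline Follow-Back (TLFB) item. Three matter here:

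- Days to first drink: "Number of days until units >0 after D0 (dosing".
- Days to first HDD: "Number of days until units ≥ 9 (male) or ≥ 7 (female) after D0 (dosing".
- Maximum units on any one day: "Max units where units >0".

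In SAP section 19.2.1, shell T_PD1a gives "Number of days after dosing to first drink" and "Number of days after dosing to first HDD" one row each, with columns n, mean, SD, median, minimum and maximum. There is no row for patients without the event. Maximum units is shown for the pre-dose window and for Days 14, 28, 56 and 84, with the change-from-baseline cells left empty.

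Two general rules apply. SAP section 9.1: "All analysis datasets will be based on observed data, except as outlined in Section 12.2". SAP section 12.1: "Missing data will not be imputed". Section 12.2 covers baseline, repeated laboratory tests and triplicate readings; it says nothing on TLFB. Neither document mentions censoring or Kaplan-Meier estimation.

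**The concern.** Both times are time-to-event outcomes. A patient who has not had the event by the end of observation carries real information, namely that the time is longer than the days observed. A plain numeric summary cannot hold that information, so the patient is left blank. Three groups are affected:

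- patients abstinent to Day 84;
- for the HDD item, patients who drink but never reach 9 units (men) or 7 units (women) in a day;
- patients who withdraw before the event. Under Protocol section 5.3, information collection stops at withdrawal.

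The summary row cannot tell an 84-day abstainer from an early withdrawal; both appear only as a smaller n.

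Maximum units has a similar gap. If the maximum is taken only over days with units above 0, a window with no drinking has no maximum. The pre-dose row should be essentially complete, since Protocol section 5.2.1 requires at least 4 HDD in the 28 days before Screening. The post-dose rows would cover drinkers only.

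**Working it through.** The plan states no figure to reproduce: it has no hypothesis test, no formal sample size and no assumed abstinence rate. The numbers below are therefore illustrations under stated assumptions.

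**1. Direction.** Every time dropped because the patient was event-free to the end of follow-up is longer than every time retained. Dropping these patients can only lower the mean and median, or at best leave the median unchanged. This needs no model. For event-free withdrawals the direction is not guaranteed in a small sample.

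**2. Size under a constant hazard.** Let S be the assumed proportion abstinent at Day 84.

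- Hazard: λ = −ln(S)/84.
- True median: ln(2)/λ.
- Median among those who drink by Day 84: −ln(1 − (1 − S)/2)/λ.

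For S = 0.25, λ = 1.3863/84 = 0.01650. The true median is 0.6931/0.01650 = 42.0 days. The drinkers-only median is −ln(0.625)/0.01650 = 28.5 days.

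| Abstinent at Day 84 | True median (days) | Drinkers-only median (days) |
|---|---|---|
| 25% | 42.0 | 28.5 |
| 40% | 63.5 | 32.7 |
| 60% | 114.0 (beyond follow-up) | 36.7 |

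**3. Size under a different pattern.** Take 12 patients with assumed first-drink days 3, 5, 7, 10, 14, 18, 21, 28, 35, 42, 56 and 70, and turn the k longest into abstainers. With k = 4 the planned mean is 106/8 = 13.25 days. Holding those four at Day 84 gives (106 + 4 × 84)/12 = 36.83 days.

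| Abstainers k | n in row | Planned mean | Mean with abstainers held at 84 | Kaplan-Meier median |
|---|---|---|---|---|
| 0 | 12 | 25.75 | 25.75 | 18 |
| 2 | 10 | 18.30 | 29.25 | 18 |
| 4 | 8 | 13.25 | 36.83 | 18 |
| 6 | 6 | 9.50 | 46.75 | 18 |
| 8 | 4 | 6.25 | 58.08 | not reached |

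In step 2 the planned figure rises as abstinence rises, but far more slowly than the truth. In step 3 it falls. The shortfall appears in both; how the planned figure moves with abstinence depends on the relapse pattern.

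**4. Maximum units, literal reading.** Assume maxima of 4, 6, 8, 10, 12, 12, 14, 16, 18, 20, 22 and 24 units, and turn the four lowest into abstainers. The planned mean is 138/8 = 17.25; counting the abstainers as 0 gives 138/12 = 11.5.

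**5. Will it arise?** If each patient abstains to Day 84 with probability p, the chance that at least one of 12 does is 1 − (1 − p)^12. For assumed p of 10%, 25% and 33% this is 72%, 97% and 99%.

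**The case against.** The strongest reply is that exclusion is inferred. The SAP never says that event-free patients are left out, a fully recorded abstainer has no missing TLFB days, and section 12.1 says that patients who withdraw are included in the analyses. That is right as far as it goes. But the SAP does not say how they are included, and it gives no number that could be entered for them. Elsewhere it does supply such conventions: values below the quantification limit are set to zero in summary statistics (section 15.1), and a missing discharge end time is replaced by the start time (section 14.8.6). Here, following the written rules leaves a blank.

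Second, abstinence is well covered elsewhere. Number of HDD, percentage of heavy drinking days, percentage of drinking days, mean units per day, percentage of abstinent days and units per week are all defined when units are 0. The TLFB listing puts these beside the two times for each patient, withdrawals are listed, and n is printed. With at most 12 patients, a careful reader could recover many event-free cases. This stands, and it limits the damage. It does not make the summary rows correct.

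Third, a programmer might enter 0 for maximum units. That is possible, so this part rests on the literal wording. Since no change from baseline is planned for this item, the claim that a planned contrast with baseline is biased upward has no support.

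**Conclusion.** The concern holds for three exploratory, descriptive items. As written, the rows for days to first drink and days to first HDD summarise only patients who had the event, and so understate event-free time. Under a constant hazard with 25% or 40% abstinent at Day 84, the median shown would be 28.5 or 32.7 days against 42.0 or 63.5. These abstinence rates and the hazard shape are assumptions. The maximum-units part is weaker because it depends on a literal reading.

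A reader might infer more, and the documents do not support it. They do not state that abstainers are excluded; that follows from the definitions together with the data rules. Nor are the alcohol-use results as a whole stripped of the best outcomes, because the companion items keep them. It is also not generally true that the planned figure hardly responds to a better outcome, or that it always moves the wrong way. Nothing is tested, and no dose or success decision is tied to these rows. The point should be corrected before database lock, but it does not threaten the study's primary conclusions.

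**What to change.** In SAP Appendix A, section 4.2, and shell T_PD1a:

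- Treat both times as time-to-event. The event is the first TLFB day after Day 0 with units above 0, or at the HDD threshold for the patient's sex. Censor at the last day covered by TLFB.
- Report the number and percentage event-free to Day 84, and separately the number censored earlier. Give the Kaplan-Meier median, or state that it was not reached. A 95% confidence interval and a restricted mean to Day 84 are optional at this sample size.
- Define maximum units as the maximum over all recorded days in the window, equal to 0 when all recorded days are 0.

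No new data are needed. The cost is SAP wording and one or two table rows or a plot. The estimates will be imprecise with at most 12 patients. Kaplan-Meier also assumes that patients who leave event-free would have relapsed like those who stay, which is why early censoring should be shown separately. The change is best made before database lock, since the SAP treats analyses added later as unplanned.
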